4.4 Duration of Study Participation

Study participation should last between six and twelve weeks. Participants are required to attend one remote screen visit and five clinic visits (second screening visit and four scanning/t-PBM sessions) and answer questions during a single follow-up phone call. If scheduled for consecutive weeks, participants will complete the study in six weeks. However, for logistical regions the time between screening completion and the first scanning/t-PBM session can be as long as four weeks; in addition, as long as two weeks may pass between each scanning/t-PMB session.

4.5.1 Research Use of Stored Human Samples, Specimens, or Data

- Intended Use: Data collected under this protocol may be used to study mood and anxiety disorders. No genetic testing will be performed.
- Storage: Samples will not be stored. Data will be stored using codes assigned by the investigators. Data will be kept in password-protected computers. Only investigators will have access to the samples and data.
- Tracking: A tracking file will link identification codes with identifying information, but this file will be password-protected and stored on a computer that can also only be accessed with a password.

4.6 Participant Withdrawal or Termination

4.6.1 Reasons for Withdrawal or Termination

Participants are free to withdraw from participation in the study at any time upon request. An investigator may terminate participation in the study if:

- Any clinical adverse event (AE), laboratory abnormality, or other medical condition or situation occurs such that continued participation in the study would not be in the best interest of the participant
- The participant meets an exclusion criterion (either newly developed or not previously recognized) that precludes further study participation
- Subject fails to adhere to protocol requirements so that the integrity of the data is compromised (e.g. subject fails to respond to attempts to schedule subsequent visits such that more than allotted time passes between scanning/treatment visits).

4.6.2 Handling of Participant Withdrawals or Termination

Every effort will be made to conduct the follow-up assessment via phone with all withdrawn or terminated participants. The phone assessment includes

If a site is unable to contact a subject or if the subject fails to appear for a visit, three documented phone calls should be made, followed by a letter (or its equivalent). The letter should detail the need for the subject to appear for a visit, the site's unsuccessful attempts to contact the subject, and that failure to contact the site will result in the subject being withdrawn from the study.

If the certified letter is returned to the site as undeliverable or the letter is delivered but the subject does not contact the site and no other contact is made with the subject or the subject's caregiver, then the subject will be considered Lost to Follow-up and discontinued from the study. All attempts to contact the subject will be documented.

4.7 Premature Termination or Suspension of Study

This study may be temporarily suspended or prematurely terminated if there is sufficient reasonable cause. Written notification, documenting the reason for study suspension or termination, will be provided by the suspending or terminating party to all investigators, and the funding agency. If the study is prematurely terminated or suspended, the PI will promptly inform the IRB and will provide the reason(s) for the termination or suspension.

Circumstances that may warrant termination or suspension include, but are not limited to:

- Determination of unexpected, significant, or unacceptable risk to participants
- Demonstration of efficacy that would warrant stopping
- Insufficient compliance to protocol requirements
- Data that are not sufficiently complete and/or evaluable
- Determination of futility

Study may resume once concerns about safety, protocol compliance, data quality are addressed and satisfy the sponsor, IRB and/or FDA.

5 Study Agent (Study drug, device, biologic, vaccine etc.) and/or Procedural Intervention

5.1 Study Agent(s) and Control Description

LightForce® EXPi Deep Tissue Laser Therapy™ System, Transcranial PhotoBioModulation-1000 (tPBM-2.0)

As described in **Section 2.2**, the tPBM-2.0 is an investigational device based on LiteCure's LightForce® EXPi Deep Tissue Laser Therapy™ System. For the investigational study, the EXPi System's beam delivery - Empower™, is modified to non-invasively deliver Near-Infrared Radiation (NIR) to subjects diagnosed with MDD. The modified system is also configured to provide sham (placebo) treatment. The device is manufactured and supplied by LiteCure LLC, [name].

The tPBM-2.0 is considered a Class II medical device per 21 CFR 890.5500 and 878.4810 and is manufactured per 21 CFR 820. It utilizes a laser diode source with a maximum continuous (CW) output of ≤30 Watts at a wavelength of 808 nanometers (nm) and nominal beam diameter of 40mm at the outside aperture.

The tPBM-2.0 operates in one of five modes: NIR low irradiance (50 mW/cm²), NIR middle irradiance (300 mW/cm²), continuoushigh irradiance (700 mW/cm²), NIR pulsedhigh radiance (peak irradiance 833 mW/cm²) and sham. The device's behavior, performance/output of all visible and audible indicators including the graphic user interface, is identical for all modes, which differ only with respect to the parameters of laser emission. In simple terms, NIR modes of the tPBM-2.0 produces laser energy; sham mode does not produce laser energy. Therefore, since the laser radiation emitted during NIR mode is invisible to the naked eye, the modes are indistinguishable from one another.

The tPBM-2.0 consists of a therapeutic laser console (that produces laser energy as NIR), and an optical delivery system consisting of a flexible, double-sheathed optical fiber connected to a custom helmet (cap). The cap is configured to deliver NIR light to EEG sites F4 and F3 (or in close proximity if covered by hair), covering a total surface treatment area of approximately 24 cm²[12 cm² x 2]. It also includes laser safety eye wear with an optical density rating >5.0 at 808 nm. Participants will be blinded to the order in which they experience each of the four modes. The treatment mode administered at each session will depend on a pre-determined randomization scheme

The therapeutic laser console is the only component of the device that is not MRI compatible. It will be stored in an equipment room located in Zone 2 (area with no detectable magnetic field but to which access is restricted due to scanner proximity). An MRI-compatible optical fiber will connect the laser console to the MRI-compatible cap. The safety eye wear is also MRI compatible.

Aside from the cap, the tPBM-2.0 is the same device as LiteCure's EXPi System – Model LTS-2500, which is marketed under FDA's 510(K) # K107637.

The cap is a custom 3D-printed headgear made of plastic and serves to hold the laser probe in place, between the MRI coil and the subject's head. The cap is provided by the device manufacturer (LiteCure) and is very similar to those used in our previous t-PBM studies. The laser probe (attached to the cap) will be connected to the laser console with a multimode MR-compatible optical fiber. The distal end of the optical fiber is fitted with ceramic ferrules, which will be affixed to the cap. The cap (headgear) contains clamps which secure the ferrules. The cap will be used in place of the wand. The cap is the only modification of the device delivery system, and it was required in order to do the t-PBM inside the MRI scanner.

The t-PBM-2.0 is a nonsignificant risk device because it:

- (1) Is NOT intended as an implant and DOES NOT present a potential for serious risk to the health, safety, or welfare of a subject;
- (2) Is NOT purported or represented to be for a use in supporting or sustaining human life and DOES NOT present a potential for serious risk to the health, safety, or welfare of a subject;
- (3) Is NOT for a use of substantial importance in diagnosing, curing, mitigating, or treating disease, or otherwise preventing impairment of human health and presents a potential for serious risk to the health, safety, or welfare of a subject; or
- (4) DOES NOT otherwise present a potential for serious risk to the health, safety, or welfare of a subject.

Further,

- The t-PBM-2.0 maximum dose administered in this study does not exceed the Maximum Permissible Exposure (MPE) for skin – Center for Devices and Radiological Health (CDRH), 21CFR1040.10 and 21CFR1040.11;
- The t-PBM-2.0 is substantially equivalent to the OmniLux New U which the FDA has already categorized as a non-significant risk device;
- Currently FDA-cleared lasers are typically available over-the-counter and are considered safe to use without professional supervision.

At NKI both research coordinators and co-investigator [name], PhD, LCSW will operate the study device and perform other procedures under the close supervision of [name] (PI). As in our previous studies with photobiomodulation at NKI, all study personnel involved in operating the laser will complete (and have valid training certificates for) the American Institute of Medical Laser Applications Medical Laser Safety training. In addition, they will be trained by the device manufacturer directly in device operation. [name], the NKI research nurse ([name]), and one of the NKI research coordinators already have experience with the device, having administered t-PBM treatments in a prior study at NKI.

5.1.1 Acquisition

The t-PBM 2.0's will be provided and shipped to sites by LiteCure®

5.1.2 Product Storage and Stability

The device(s) will be stored in MRI equipment rooms at NKI and MGH. These rooms are secure and well-ventilated and have fire extinguishers readily available. The devices will be placed on flat hard surfaces with adequate airflow (including a minimum of 10cm clearance around the back of the device).

5.1.3 Dosing and Administration

Across the four visits participants experience one session each of: 1) sham t-PMB; 2) low-irradiance t-PBM; 3) middle-irradiance t-PBM; and 4) high-irradiance t-PBM. The sequence in which the particular t-PBM parameters (summarized in Table 1) are utilized will be random; both participant and study staff will be blind to the parameters.

5.1.4 Duration of Therapy

Participants will undergo three sessions of active and one session of sham t-PBM, all during MR scanning. The duration of irradiation is 0, 3.33 or 20 minutes, depending on randomization; however, each session will last a total of 20 minutes to maintain blinding.

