2.4 Dose Rationale

As depicted in Table 1, all t-PBM sessions will incorporate: **1.** laser light with **2.** a wavelength of 808nm, corresponding to the absorption peak of the primary photoreceptor cytochrome-C oxidase **3.** and target bilaterally the dlPFC (standard EEG electrode sites F4, F3). The total area of exposure, as a result, will also remain constant at 24cm² (12 cm² bilaterally).

The irradiance will vary across three experimental doses (50, 300, and \geq 700 mW/cm²) therefore also impacting the exposure time, fluence, and total energy. The low and medium doses will both be administered in continuous wave mode; the high dose will be administered in pulsed wave mode (\geq 700mW/cm²). .

Rationale for Constant t-PBM parameters: We will use a laser source of NIR since, in contrast to LED devices, lasers on optic fibers are MRI-compatible and can more easily produce high irradiation (e.g. 700 mW/cm²). The 808 nm NIR wavelength is at the absorption peak of the primary photoacceptor cytochrome-C oxidase⁵⁵, has optimal penetration through the skull^{12,14}, and proven effects on CBF (BOLD signal)¹⁰³ and on mood^{30,35}. We chose to broadly irradiate and engage the PFC, since: 1) the aforementioned areas are all involved in emotion-regulation processes⁹⁹; 2) abnormalities in CBF, which are well-documented in MDD patients, involve broadly PFC^{38,39,41}.

Rationale for Irradiance Doses: t-PBM at irradiance doses of 50 mW/cm² had significant effects on mood^{29,30} and cognition¹⁰⁸; t-PBM at 300 mW/cm² have been associated with changes in CBF¹⁰³ and on cognition^{107,109}, while irradiance doses of 700 mW/cm² have been effective in depression³⁰ and in large studies in stroke^{21,22,100}. All three doses have been safely used in adults. Therefore, the three irradiance doses proposed (50, 300, and \geq 700 mW/cm²) cover the full spectrum of doses in the literature, enabling us to determine the optimal dose for target engagement

Rationale for Wave Form Selection: We will use continuous wave (CW) NIR for the low and medium doses, which is supported by a preponderance of current data..

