We will use a pulse wave for the high dose because pulsing can prevent skin warming and discomfort thus facilitating enrollment and retention and safeguarding the integrity of the single blind. Safety data from three previously referenced stroke RCTs including 1,410 participants^{21, 22, 100} offer ample evidence that a 700 mW/cm² continuous wave dose is safe. However, testing during the development of our study-specific device suggests that some participants may experience it as “hot” and/or unpleasant and be able to distinguish it from the sham and lower doses. Offering the pulsed high dose instead allows us to expose participants to a similar peak irradiance while lowering the average irradiance, thus reducing the likelihood of inducing skin warming or discomfort.

Table 1. t-PBM Parameters Across 4 Sessions

Parameters	Dose				
	High	Middle	Low	Sham	
Peak Irradiance (mW/cm ²)	833	300	50	0	
Average Irradiance (mW/cm ²)	275	300	50	0	
Time Irradiation (s)	600	333	1200	0	
Average Fluence (J/cm ²)	165	100	60	0	
Total energy (kJ/ cm ²)	2.0	2.4	1.4	0	
Wave Mode	Pulsed	Continuous	Continuous	N/A	
NIR source	Laser	Laser	Laser	N/A	
Wavelength	808nm	808nm	808nm	N/A	
Area of exposure	24cm ²	24cm ²	24cm ²	N/A	
Anatomical targets	F4, F3	F4, F3	F4, F3	F4, F3	

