3.1 Primary Objective

Our primary objective is to identify the t-PBM irradiance dose (50, 300, or ≥ 700 mW/cm 2) with the largest impact on PFC CBF in MDD.

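### Section 5.1.4 gives irradiation times of 0, 3.33 or 20 minutes, but Table 1 gives 10, 5.55, 20 and 0 minutes; Table 1's High energy entry and its energy unit are also inconsistent

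*Combined protocol and SAP*

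**What the plan says.** Section 5.1.4 (Duration of Therapy) lists three durations for the four modes: "The duration of irradiation is 0, 3.33 or 20 minutes, depending on randomization". It ties none of them to a mode. The same sentence fixes every session at 20 minutes so that session length does not reveal the mode.

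Section 5.1.3 sends the reader elsewhere for the settings: "The sequence in which the particular t-PBM parameters (summarized in Table 1) are utilized will be random". The paragraph on t-PBM sessions in section 6.2.3 makes the same reference to Table 1. The Table 1 row that begins "Time Irradiation (s" gives 600, 333, 1200 and 0 for High, Middle, Low and Sham. The row that begins "Total energy (kJ" is labelled kJ/cm² and gives 2.0, 2.4, 1.4 and 0.

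Section 2.4 says that irradiance varies across the three active doses, "therefore also impacting the exposure time, fluence, and total energy". On area it says: "The total area of exposure, as a result, will also remain constant at" 24 cm², made up of 12 cm² on each side. Table 1 repeats 24 cm² for every active mode.

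Two other places might have settled the times but do not. Section 5.1 ("The tPBM-2.0 operates in one of five modes") lists the modes by irradiance only. Section 9.5.1 says the randomized order is programmed into each site's device, without giving programmed times.

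**The concern.** Section 5.1.4 is the operative statement of how long the laser is on, and Table 1 is the cited summary of the same settings. They should agree mode by mode, and for two of the three active modes they do not.

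The objective reads "Our primary objective is to identify the t-PBM irradiance dose" with the largest effect on prefrontal blood flow. The doses are named by irradiance, but section 2.4 says that exposure time, fluence and total energy change with it. A dose chosen at the end of the study can be described and repeated only if its irradiation time is known. As written, someone following 5.1.4 literally would use a 3.33-minute exposure that Table 1 does not contain, and would find no entry for 10 or 5.55 minutes.

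**Working it through.** **Inputs.** Times, peak and average irradiance, fluence, total energy and area come from Table 1 (area also from the text of section 2.4). The durations 0, 3.33 and 20 minutes come from section 5.1.4.

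**Step 1: times in minutes (seconds / 60).**

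| Mode | Table 1 (s) | Minutes | Listed in 5.1.4? |
|---|---|---|---|
| High | 600 | 10.0 | no |
| Middle | 333 | 5.55 | no |
| Low | 1200 | 20.0 | yes |
| Sham | 0 | 0 | yes |

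In the other direction, 3.33 min × 60 = 199.8 s, which is not a Table 1 time.

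**Step 2: does Table 1's time row agree with its fluence row?** Fluence (J/cm²) = average irradiance (mW/cm²) × time (s) / 1000.

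- High: 275 × 600 / 1000 = 165.0 (printed 165)
- Middle: 300 × 333 / 1000 = 99.9 (printed 100)
- Low: 50 × 1200 / 1000 = 60.0 (printed 60)

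The two rows agree, so the time row is not garbled in extraction. High's 600 s is elapsed irradiation time at average irradiance. Using the peak would give 833 × 600 / 1000 = 499.8 J/cm², and session time is ruled out because every session lasts 20 minutes.

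**Step 3: can 3.33 minutes be reconciled with Table 1?**

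- *A slip for Middle's 333 s.* High's 10 minutes would still be missing from 5.1.4. Taken literally for Middle, 200 s would give 300 × 200 / 1000 = 60 J/cm² against 100 printed.
- *Laser-on time of the pulsed High mode.* The on-fraction is 275 / 833 = 0.330, and 600 × 275 / 833 = 198 s, or 3.30 minutes. This is numerically close, but no text defines such a time, and Middle's 5.55 minutes would still be missing.

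Neither reading makes the two places agree.

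**Step 4: energy row.** Total energy (kJ) = fluence (J/cm²) × area (cm²) / 1000.

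| Mode | Fluence × 24 cm² | Printed | Fluence × 12 cm² |
|---|---|---|---|
| High | 165 × 24 / 1000 = 3.96 | 2.0 | 1.98 |
| Middle | 100 × 24 / 1000 = 2.40 | 2.4 | 1.20 |
| Low | 60 × 24 / 1000 = 1.44 | 1.4 | 0.72 |

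Middle and Low fit 24 cm². High fits only 12 cm², the one-side area. Per cm², the values would be 0.165, 0.100 and 0.060 kJ/cm². The printed figures are therefore totals in kJ, and the kJ/cm² label does not fit them.

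**The case against.** The strongest case on the other side is that this is a text slip of little consequence. Doses are named by irradiance, the primary model in section 9.3.2 treats dose as four categories, and the sample size in section 9.4 uses no exposure time. No analysis described in section 9 uses total energy. All of that stands, and it limits the point to the description and delivery of the doses.

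It can also be said that Table 1 is the cited summary and agrees with its own fluence row, so a reader might infer that its times are the intended ones and that 5.1.4 can be ignored. The internal agreement is a fact, but no text gives Table 1 precedence. Choosing between two statements of exposure is for the sponsor.

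A reader might infer more in other directions:

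- *That some mode is under-exposed by a stated percentage.* Section 5.1.4 assigns 3.33 minutes to no mode, so any such percentage depends on a pairing that the document does not make.
- *That participants received wrong exposures.* The programmed times are not reported, so the documents cannot show this.
- *That High really delivers more energy than Middle.* The 3.96 kJ figure holds only if the printed fluence and 24 cm² are both right. The match at 12 cm² suggests where the 2.0 may have come from but does not prove it.

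**Conclusion.** The contradiction holds. Two of Table 1's four irradiation times (High 10 minutes, Middle 5.55 minutes) are absent from section 5.1.4, and one of the three times in 5.1.4 (3.33 minutes) is absent from Table 1. This rests only on the printed figures and on unit conversion, and nothing in the document resolves it.

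The energy row is a secondary inconsistency. With the printed fluence and area held fixed, High comes to 3.96 kJ, 1.98 times the printed 2.0. The documents do not show which High entry is at fault. The unit is wrong for all three active modes.

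The consequence is confined to how each dose is delivered, reported and reproduced. A reader might infer that the primary analysis is compromised. The documents do not support that, because the categorical dose comparison does not use these figures. The correction is worth making because the conflict sits in the treatment section and is cheap to remove.

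**What to change.** The sponsor should reconcile section 5.1.4, Table 1 and the settings programmed in each site's device. One irradiation time per mode should then be stated, by mode name and identically, in 5.1.4 and Table 1. The High column should be made consistent across time, average irradiance, fluence, area and total energy, and the energy row should carry the unit that its values have. No time, energy or dose is proposed here.

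The cost is a protocol text and table correction plus a check of device settings at the two scanning locations (NKI and MGH). The settings check is a precaution. It is sensible because section 5.1 describes the device's visible and audible behaviour as the same in every mode, so routine observation may not reveal a discrepancy. No change to design, sample size or analysis is needed.

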5.2 Study Agent Accountability Procedures

LiteCure will ship one device each to NKI and MGH. Sites will document the date and condition of the devices at reception and eventual return (via mail) at study conclusion.

6 Study Procedures and Schedule

6.1 Study Procedures/Evaluations

Note that as many procedures as possible can and will be conducted remotely, via telephone or WebEx. Procedures marked with an asterisk (*) will require in person clinic visits.

6.1.1 Study Specific Procedures versus Standard Clinical Care

All procedures described in sections 6.2 and 6.3 will be performed as part of the study. None are part of standard clinical care.

6.2 Study Schedule

6.2.1 Screening Phase

Duration: Up to 4 weeks, usually requires 1 remote session and 1 clinic visit.

(Additional visits may be required to repeat laboratory testing in the case of suspect results, etc.)

Study staff will:

- Obtain informed consent of potential participant verified by signature on written informed consent for screening form.
 - If the first screen visit occurs remotely, the staff will obtain informed consent of the participant via WebEx (for explanation and discussion of form) and eConsenting via RedCap.
- Obtain contact and demographic information required for study participation.
- Administer the Montreal International Neuropsychiatric Interview (MINI), the Inventory for Depressive Symptomatology, Clinician-Rated scale (IDS-C), the Montreal Cognitive Assessment (MoCA), the Antidepressant Treatment Resistance Questionnaire (ATRQ), the MRI safety checklist,

and the Columbia Suicide Severity Risk Scale (C-SSRS), to determine eligibility based on inclusion/exclusion criteria.

- Administer the NIS-Skin Color Scale (NIS-SCS).
- Review medical history to determine eligibility based on inclusion/exclusion criteria.
- Review concomitant medications and therapies to determine eligibility based on inclusion/exclusion criteria.
- *Perform medical examinations needed to determine eligibility based on inclusion/exclusion criteria (includes recording vital signs).
- *Collect blood (if indicated)/urine for laboratory testing to determine eligibility based on inclusion/exclusion criteria (see section 6.2.2).
- *Test study device fit.
- Verify inclusion/exclusion criteria.

Schedule study visits for participants who are eligible and available for the duration of the study. Test Fit: Study staff will introduce the participant to the study device and confirm that they will be able to fit comfortably in the scanner while wearing it. We will exclude any participant who cannot fit.

